11. ADVERSE EVENTS

The PI and clinical facility staff are responsible for detection, recording and reporting of events that meet the criteria and definition of various AEs as listed below. Adverse events will be recorded from time of signed consent through to EOS; only AEs that occur post-dose will be considered treatment-emergent. The PI and clinical facility staff are responsible for detection, recording and reporting of pregnancy and appropriate follow up. Any known pregnancy that occurs within 90 days following the end of study visit should be reported by the subject to the PI. Information regarding any reported pregnancy should be collected for at least 1 year after birth or longer if it is decided that additional follow-up is required or until the end of the pregnancy.

11.1. Definitions

An **Adverse Event (AE)** is any untoward medical occurrence in a patient or clinical investigation patient administered a pharmaceutical product and which does not necessarily have to have a causal relationship with this treatment. An AE can therefore be any unfavorable and unintended sign (including an abnormal laboratory finding or diagnostic test), symptom, or disease temporally associated with the use of a medicinal (investigational/experimental) product, whether related to this product or not. (Refer to ICH E2a: Clinical Safety Data Management: Definitions and Standards for Expedited Reporting, 27 October 1994).

Treatment-emergent AEs will be defined as AEs with onset after administration of the study drug, or when a pre-existing medical condition increases in severity or frequency after study drug administration.

AEs will not include:

- A medical procedure such as surgery, endoscopy, tooth extraction, or transfusion (although the condition that leads to the procedure may be an AE)
- A pre-existing disease or condition present at the start of the study that does not worsen during the study
- Any situation where an untoward medical occurrence has not occurred (for example, hospitalizations for cosmetic elective surgery or “social” admissions)
- An overdose of either the investigational product or a concurrent medication without any resulting signs or symptoms

A **Serious Adverse Event (SAE)** is an AE that:

- Results in death

- Is life-threatening (NOTE: The term ‘life-threatening’ in the definition of ‘serious’ refers to an event/reaction in which the participant was at immediate risk of death at the time of the event/reaction; it does not refer to an event/reaction which hypothetically might have caused death, if it were more severe)
- Requires inpatient hospitalization or prolongation of an existing hospitalization
- Results in persistent or significant disability/incapacity
- Is a congenital anomaly/birth defect
- Is a medically important event or reaction

Medical and scientific judgment should be exercised in deciding whether other situations should be considered serious such as important medical events that may not be immediately life-threatening or result in death or hospitalization but might jeopardize the participant or might require medical or surgical intervention to prevent one of the other serious outcomes listed in the above definition. These should also be considered serious. Examples of such events are intensive treatment in an emergency room or at home for allergic bronchospasm, blood dyscrasias or convulsions that do not result in hospitalization, or development of drug dependency or drug abuse.

11.2. Clinical Laboratory Abnormalities and Other Abnormal Assessments as AEs

Abnormal assessments (e.g., ECGs and vital signs) that are judged by the PI as clinically significant (CS) or result in clinical sequelae will be recorded as AEs. Laboratory abnormalities will be reported by the PI as AEs if the abnormality is considered CS or results in clinical sequelae. All laboratory abnormalities reported as AEs should be recorded as CS in the laboratory database.

Clinically significant abnormal laboratory findings or other CS abnormal assessments that are detected during the study or are present at baseline and significantly worsen following the start of the study will be reported as AEs.

The PI (or medically qualified designee) will exercise his or her medical and scientific judgment in deciding whether an abnormal laboratory finding or other abnormal assessment is CS.

11.3. Timing, Frequency, and Method of Detecting AEs

Any pre-existing conditions or signs and/or symptoms present in a participant prior to the start of the study (i.e., before informed consent) should be recorded as Medical/Surgical History.

All AEs occurring after informed consent and on or before the final visit must be reported as AEs; only AEs that occur post-dose will be considered treatment-emergent. All AEs must be recorded irrespective of whether they are considered drug-related. AEs will be collected through the EOS.

At each visit/assessment in the period defined above, AEs will be evaluated by the PI (or medically qualified designee) and recorded.

11.4. Recording of AEs

When an AE occurs, it is the responsibility of the PI or medically qualified designee to review all documentation (e.g., hospital progress notes, laboratory, and diagnostics reports) relative to the event. The PI or medically qualified designee will then record the AE on the AE CRF. Additional reporting requirements for an AE that meets serious criteria are

discussed in Section 11.7 below.

The PI or medically qualified designee will attempt to establish a diagnosis of the event based on signs, symptoms, and/or other clinical information. In all cases, when available, the diagnosis should be reported as the event and not the individual signs/symptoms. It is not acceptable for the PI to send photocopies of the patient's medical records to the Sponsor in lieu of completion of the appropriate AE eCRF pages.

11.5. Evaluating AEs

11.5.1. Assessment of Severity

The PI or medically qualified designee will assess severity for each AE reported during the study. The assessment will be based on the PI's (or medically qualified designee's) clinical judgment. The severity of all AEs should be assigned to one of the following categories:

- Mild: An event that is easily tolerated by the participant, causing minimal discomfort and not interfering with everyday activities.
- Moderate: An event that is sufficiently discomforting to interfere with normal everyday activities.
- Severe: An event that prevents normal everyday activities.

An AE that is assessed as severe should not be confused with an SAE. Severity is a category utilized for rating the severity of an event; and both AEs and SAEs can be assessed as severe. An event is defined as 'serious' when it meets one of the predefined outcomes as described in Section 11.1.

11.5.2. Assessment of Causality

The PI (or medically qualified designee) is obligated to assess the relationship between investigational product and the occurrence of each AE. The PI (or medically qualified designee) will use clinical judgment to determine the relationship. Alternative causes, such as natural history of the underlying diseases, concomitant therapy, other risk factors, and the temporal relationship of the event to the investigational product will be considered and investigated. The PI (or medically qualified designee) will also consult the Investigator's Brochure in the determination of his/her assessment.

There may be situations when an SAE has occurred and the PI has minimal information to include in the initial SAE report. However, it is very important that the PI (or medically qualified designee) always assess causality for every event prior to transmission of the SAE report form. The PI (or medically qualified designee) may change his/her opinion of causality considering follow-up information, amending the SAE report form accordingly. The causality assessment is one of the criteria used when determining global regulatory reporting requirements.

The PI (or medically qualified designee) will provide the assessment of causality utilizing three possible categories: Not Related, Possibly Related and Probably Related.

An AE will be considered "not related" to the use of the product if any of the following tests are met:

- An unreasonable temporal relationship between administration of the product and the onset of the AE (e.g., the event occurred either before, or too long after administration of the product for it to be considered product-related)
- A causal relationship between the product and the AE is biologically implausible (e.g.,

death as a passenger in an automobile accident)

- A clearly more likely alternative explanation for the AE is present (e.g., typical adverse reaction to a concomitant drug and/or typical disease-related event)

An AE will be considered “Possibly related” when an event follows a reasonable temporal sequence from administration of the study drug, but which could also be explained by concurrent disease or other drugs or chemicals. Or an event that follows a known or expected response pattern to the drug but that could have been produced by a number of other factors.

An AE will be considered “Probably related” when an event follows a reasonable temporal sequence from administration of the IP, unlikely to be attributed to concurrent disease or other drugs or chemicals. Also, an event that follows a known or expected response pattern to the IP, or that is confirmed by stopping or reducing the dosage of the IP and that could not reasonably be explained by known characteristics of the participant’s clinical state.

11.6. Follow-up of AEs

After the initial AE, the PI is required to proactively follow each participant and provide further information on the participant’s condition as deemed appropriate.

All AEs will be followed until resolution, until the condition stabilizes, until the event is otherwise explained, or until the participant is lost to follow-up. Once resolved, the appropriate AE eCRF page and SAE report form (if event is serious) will be updated. The PI, or medically qualified designee, will ensure that follow-up includes any supplemental investigations as may be indicated to elucidate the nature and/or causality of the AE or SAE. This may include additional laboratory tests or investigations, histopathological examinations, or consultation with other health care professionals. In the event of a fatal outcome in an SAE, the PI, or medically qualified designee, will attempt to obtain postmortem findings, including histopathology, and provide all additional information in a follow up SAE report.

New or updated information regarding an SAE will be recorded on a new SAE report form marked as follow-up with the appropriate follow-up number added to the report. The follow-up report will be signed and dated by the PI.

11.7. Prompt Reporting of SAEs

Any AE meeting serious criteria MUST be reported promptly to the Sponsor’s designated Pharmacovigilance Contract Research Organization (CRO), and the IRB/EC in accordance with applicable local/ institutional requirements.

11.7.1. Completion and Transmission of the SAE reports

Once an Investigator becomes aware that an SAE has occurred in a study participant, she/he will report the information on an SAE report form to the designated Pharmacovigilance CRO within 24 hours. The SAE report form will always be completed as thoroughly as possible with all available details of the event and signed by the PI (or medically qualified designee). If the PI does not have all information regarding an SAE, he/she will not wait to receive additional information before reporting the event. The SAE report form will be updated when additional information is received.

The PI (or medically qualified designee) will always provide an assessment of causality at the time of the initial report as described in Section 11.5.2. However, as new information becomes

available, causality may be modified.

Email transmission of the SAE report form are the preferred methods to transmit this information to the designated Pharmacovigilance CRO. Facsimile is acceptable if email is unavailable. In rare circumstances, notification by telephone is acceptable, with a copy of the SAE report sent by overnight mail. Initial notification via the telephone does not replace the need for the PI, or medically qualified designee, to complete and sign the SAE report form within the outlined time frames.

The Sponsor will provide a list of project contacts for SAE receipt, fax numbers, telephone numbers, and mailing addresses. Any event that in the opinion of the PI may be of immediate or potential concern for the participant's health or well-being will be reported to the Sponsor emergency contact listed below.

Primary Sponsor Emergency Contact	
[REDACTED]	
Back-up Sponsor Emergency Contact	
[REDACTED]	

11.7.2. Pregnancy Reporting

Pregnancy occurring in a participant or in the female partner of a male participant during the study (or within 90 days following EOS) must be reported on a pregnancy reporting form or on an SAE form to the designated Pharmacovigilance CRO within 24 hours of initially becoming aware of the pregnancy by the Investigator.

Pregnancies are not SAEs. However, pregnancy data will be collected at the initial notification, birth/termination of pregnancy, and for at least 1 year after birth or longer if it is decided that additional follow-up is required or until the end of the pregnancy.

Any SAE that occurs during pregnancy (eg, serious maternal complications, therapeutic abortion, ectopic pregnancy, stillbirth etc.) must be reported in accordance with the procedure for reporting SAEs.

11.7.3. Serious Adverse Event Reports to the IRB

The PI, or responsible person per local requirements, will comply with the applicable local regulatory requirements related to the reporting of SAEs to regulatory authorities and the appropriate EC/IRB.

11.8. Regulatory Requirements for Reporting of SAEs

The PI (or medically qualified designee) will promptly report all SAEs in accordance with the procedures detailed in Section 11.7. Prompt notification of SAEs by the PI is **essential** so that the Sponsor may comply with its regulatory obligations.

Any SAEs requiring expedited reporting will be reported by the Sponsor to relevant regulatory authorities, Investigators, and IRBs/ethics committee in accordance with the Sponsor's procedures and local regulatory requirements.

11.9. Post-study AEs

A post-study AE is defined as any event that occurs outside of the AE detection period defined in Section 11.3.

Investigators are not obligated to actively seek AEs in former study participants. However, if the Investigator learns of any SAE at any time after a participant has been discharged from the study, and he/she considers the event reasonably related to the investigational product, the PI will promptly notify the Sponsor.

11.10. SAEs Related to Study Participation

An SAE considered related to study participation (e.g., procedures, invasive tests, a change in existing therapy), even if it occurs during the pre- or post-treatment period, will be reported promptly (refer Section 11.7).

12. DATA ANALYSIS AND STATISTICAL CONSIDERATIONS

In general, continuous data will be summarized by descriptive statistics, including number of subjects, mean, standard deviation, median, minimum, and maximum. Categorical data will be summarized by the number and percentage of subjects. Specifics of data analysis are provided in the Statistical Analysis Plan.

[figure not shown]
12.1. Sample Size Considerations & Stratification

Sample sizes for NHV cohorts 1-5 and CF cohorts 2b, 3b, and 4b are decided based on the probability of observing at least one TEAE from each cohort. When probability of observing TEAE from a single subject who received active drug is 30%, chance of observing at least one TEAE will be higher than 75%, among 4 dosed subjects. With cohort size 8 or 9 (cohorts 4b and 5), probability of seeing at least one TEAE would be approximately 85% and 95% if assumed probabilities of observing AE from a single dosed subject are 20% and 30%, respectively. Table 5 below lists probabilities of observing at least one TEAE under various scenarios.

Table 5: Sample Size Calculation for Cohorts 1-5 and 2b, 3b and 4b

Probability of observing at least one TEAE from each dosed subject	Number of subjects treated per Cohort	Probability of observing at least one TEAE from Cohort
0.2	4	0.59
0.3	4	0.76
0.2	5	0.67
0.3	5	0.83
0.2	6	0.74
0.3	6	0.88
0.2	7	0.79
0.3	7	0.92
0.2	8	0.83
0.3	8	0.94

Probability of observing at least one TEAE from each dosed subject	Number of subjects treated per Cohort	Probability of observing at least one TEAE from Cohort
0.2	9	0.87
0.3	9	0.96
0.2	10	0.89
0.3	10	0.97

Figure 2: Relationship between Sample Size and Probability of Observing at Least One TEAE

Sample size for cohort 6 is calculated to have more than 80% power to observe 5% absolute change from baseline in ppFEV1 at Day 43 at significance level 0.05, with standard deviation 7%. Sub-group analysis of CF patients will be conducted according to the presence of CFTR modulator/corrector use at baseline as well as inhaled hypertonic saline use at baseline.

No stratification is planned in this study.

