- Discontinuation of a subject or group of subjects from the study
- The study is stopped immediately with no further dosing
- The study will continue until the current cohort is completed
- The study will continue, but the next dose escalation will be to a level midway between the current level and the next planned level
- The study will continue as planned

The DSC will consist of at least the Sponsor Medical Monitor, Sponsor pharmacovigilance lead, one study Investigator and an independent physician experienced in Phase 1 clinical trials.

Study Assessments:

Safety Assessments:

Safety assessments will be performed at specified time points per the SOA and will include the following:

- Vital signs: Resting heart rate, semi-supine systolic/diastolic blood pressure, respiratory rate, pulse oximetry and temperature
- Clinical laboratory measurements (e.g., biochemistry, hematology, coagulation, urinalysis), urine electrolytes including potassium, sodium and urine FeNa (spot urine electrolytes will only be analyzed in the setting of hyperkalemia)
- Resting ECG measurements (measured after participant is semi-supine for at least 3 minutes).
- Chest X-ray (upright and lateral)
At each visit, participants will be asked about concomitant medications/therapy and will be instructed to volunteer any information regarding AEs and SAEs that he/she may have experienced. Any known untoward event that occurs beyond the AE reporting period that the PI considers an SAE possibly related to study treatment will be reported to Arrowhead.
- Spirometry conducted as per ATS/ERS guidelines

Assessment of Pharmacodynamic Effect in NHVs:

- α ENaC expression from bronchial brushing and BAL samples (only assessed in NHV cohort 5)

Assessments of Efficacy in CF patients:

Results including absolute change, percent change from baseline to EOS will be analyzed and summarized by dose cohort and treatment group for efficacy parameters.

Efficacy assessments will be performed at specified time points per the SOA and will include the following:

- Spirometry
- LCI
- CFQ-R
- Rate of pulmonary exacerbations
- BMI

Immunogenicity:

Blood samples for the anti-drug antibodies test will be collected per the SOA.

Genotype:

Genotype will be obtained for CFTR and ENaC (where available) mutations.

Pharmacokinetics:

Blood samples will be collected from each subject for pharmacokinetic analysis per the SOA.

Excretion and Metabolism:

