## 2.2 Hypotheses and/or Estimations

No formal hypothesis testing will be performed.

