### 3.2 Sample Size

Sample sizes for NHV Cohorts 1-5 and CF cohorts 2b, 3b, and 4b are decided based on the probability of observing at least one TEAE from each cohort. When probability of observing TEAE from a single subject who received active drug is 30%, chance of observing at least one TEAE will be higher than 75%, among 4 dosed subjects. With cohort size 8 or 9 (Cohorts 4b and 5), probability of seeing at least one TEAE would be approximately 85% and 95% if assumed probabilities of observing AE from a single dosed subject are 20% and 30%, respectively. The table below lists probabilities of observing at least one TEAE under various scenarios.

Table 5 from Protocol: Sample Size Calculation for Cohorts 1-5 and 2b, 3b and 4b

Probability of observing at least one TEAE from each dosed subject	Number of subjects treated per Cohort	Probability of observing at least one TEAE from Cohort
0.2	4	0.59
0.3	4	0.76
0.2	5	0.67
0.3	5	0.83
0.2	6	0.74
0.3	6	0.88
0.2	7	0.79
0.3	7	0.92
0.2	8	0.83
0.3	8	0.94
0.2	9	0.87
0.3	9	0.96
0.2	10	0.89
0.3	10	0.97

Figure 2 from Protocol: Relationship between Sample Size for a Cohort and Probability of Observing at Least One TEAE within a Cohort

Sample size for Cohort 6 is calculated to have more than 80% power to observe 5% absolute change from baseline in ppFEV1 at Day 43 at significance level 0.05, with standard deviation 7%.

No stratification is planned in this study.

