## 4. COVARIATES AND SUBGROUPS

### 4.1 Planned Covariates

There are no predetermined covariates.

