## **9. STATISTICAL METHODS OF ANALYSIS**

For all summary tables and figures described in this SAP, NHV Cohorts 1-5 and CF patient Cohorts 2b-4b and 6 will be summarized separately. Subjects will be grouped by dose and dosing regimen within each table and figure, with subjects receiving placebo pooled across cohorts. All data will be combined in listings, which will be sorted by cohort and subject number.

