### **9.1 General Considerations**

Descriptive statistics will be provided for selected demographic, safety, PK, and efficacy data. Descriptive statistics of continuous data will include the number of subjects, mean, median,

---

standard deviation, minimum & maximum. Descriptive summaries of categorical data will use frequency counts and percentages. Graphical summaries of the data may be also presented.

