### **9.6.1 Spirometry**

Spirometry will be evaluated in NHVs and CF patients. In general, spirometry for NHVs are considered a safety measurement and spirometry for CF patients are considered both a safety and efficacy measurement. For CF patient cohorts, use of an inhaled bronchodilator will be recorded at each spirometry assessment. All CF patient spirometry summaries will identify use of an inhaled bronchodilator as recorded on the Spirometry eCRF.

---

Descriptive statistics summaries of pulmonary function parameters obtained from the spirometry assessments will be provided by scheduled timepoint. Absolute changes and percentage changes from baseline will be included. In addition to an overall summary, subgroup analyses (as defined in Section 4.2) will be provided.

A sensitivity analysis of FEV1 and ppFEV1 will be performed for CF patient cohorts if use of an inhaled bronchodilator at any post-baseline assessment does not match use of an inhaled bronchodilator at the baseline assessment for any CF patients. The sensitivity analysis will consist of a summary of FEV1 and ppFEV1 values with absolute and percent changes from baseline by scheduled visit, excluding any post-baseline spirometry assessments where the bronchodilator status does not match the bronchodilator status at baseline. Subgroup analyses will not be provided for the sensitivity analysis.

Plots of mean (+/- SD) FEV1 (L) and ppFEV1 (%) over time will be provided by study day from baseline to the EOS visit. Plots for CF patient cohorts will additionally include a plot from baseline to Day 37 (Cohorts 2b-4b) and a plot from baseline to Day 43 (Cohort 6).

Additionally, a plot will be provided for CF patient cohorts to visually assess the relationship between baseline sweat chloride level and ppFEV1 absolute change from baseline value. For Cohorts 2b-4b, the Day 37 ppFEV1 absolute change from baseline value will be used. For Cohort 6, the Day 43 ppFEV1 absolute change from baseline value will be used. Pearson correlation coefficients may be provided within the plot.

All pulmonary function data obtained from the spirometry assessment will be listed by subject.

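### Cohort 6 is randomised 18:6 and sized on Day 43 ppFEV1, but no active-minus-placebo estimate is planned; the >80% power is a within-group figure and should be labelled as such

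*Protocol*

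**What the plan says.** Protocol 12.1 gives the basis for the cohort's size: "Sample size for cohort 6 is calculated to have more than 80% power to observe 5% absolute change from baseline in ppFEV1". The visit used is Day 43, alpha is 0.05 and the SD is taken as 7%. SAP 3.2 repeats it: "Sample size for Cohort 6 is calculated to have more than 80% power to observe 5% absolute change from baseline in ppFEV1". Neither place gives the test, the number of patients entered into the calculation, the sidedness, or whether 7 is the SD of the change or of a single visit.

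Protocol Table 4 describes Cohort 6 as double-blind, up to 24 patients, 18 active and 6 placebo. Protocol 7.1 gives its purpose as assessing both safety and efficacy of the alternate regimen. Protocol 7.5 and SAP 7.3 time the primary analysis by its Day 43 visit. Protocol 7.5 adds that the sponsor is then unblinded to analyse efficacy as well as safety.

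On the analysis side, SAP 2.2 states "No formal hypothesis testing will be performed" and SAP 4.1 states "There are no predetermined covariates". SAP 9.1 sets the summary format: "Descriptive statistics of continuous data will include the number of subjects, mean, median", SD and range. For spirometry, SAP 9.6.1 adds "Absolute changes and percentage changes from baseline will be included". The protocol synopsis says results will be "analyzed and summarized by dose cohort and treatment group for efficacy parameters", and SAP 9 groups patients by dose and regimen, "with subjects receiving placebo pooled across cohorts". Protocol 12.6 is descriptive as well. None of these sections plans a difference between active and placebo in ppFEV1, or an interval for one.

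**The concern.** Cohort 6 is the only cohort sized on an efficacy measure; the others are sized on the chance of seeing at least one treatment-emergent adverse event. A change from baseline in the active arm alone mixes any drug effect with regression to the mean, repeated testing and period effects. Randomisation is what separates these, and the randomised contrast is the one quantity the tables will not show.

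Two things are at stake. The sponsor will look at Cohort 6 efficacy unblinded without a pre-specified estimate of the randomised effect or a statement of its precision. And a power figure above 80%, attached to a placebo-controlled cohort, can easily be taken for power against placebo.

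**Working it through.** **Inputs.** Effect 5 points, alpha 0.05, SD 7 (Protocol 12.1, SAP 3.2). Arms 18 and 6 (Protocol Table 4). Complete data. The documents give no sidedness and no definition of the SD; two-sided tests and 7 as the SD of the change are assumed unless stated otherwise.

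**1. Reproducing the plan's figure.** One-sample t-test on change from baseline, noncentrality = 5 × √n / 7.
- n = 18: 5 × 4.243 / 7 = 3.03 on 17 df, power 81.5%.
- n = 17: power 79.0%.

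So 18, the planned number of active patients, is the smallest n above 80%. Other within-group readings also exceed 80% (one-sided with n = 14: 81.2%; two-sided with n = 24: 91.8%). The basis can therefore be inferred but is not stated.

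**2. What the same inputs give against placebo.**
- SE of the difference = 7 × √(1/18 + 1/6) = 7 × 0.4714 = 3.30.
- Noncentrality = 5 / 3.30 = 1.52 on 22 df, power 30.5%.
- Power of 80% for 18 v 6 would need an SD of change of about 3.62. If 7 were a single-visit SD, SD of change = 7 × √(2(1 − ρ)), where ρ is the correlation between baseline and Day 43. Setting this to 3.62 gives ρ ≈ 0.87. The documents give no correlation.

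**3. Does pooling placebo help?** The CF cohorts plan 2 + 2 + 3 + 6 = 13 placebo patients, and 18 v 13 would give 47.5%. But the schedule for Cohorts 2b–4b (Protocol Table 1.3) has visits at Day 37 and Day 57 and none at Day 43. A by-visit Day 43 column would hold only the 6 Cohort 6 placebo patients, unless the table shells (not in these documents) align Day 37 with Day 43.

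**4. Precision of the missing estimate, unadjusted.** 95% CI half-width = t(22) × SE = 2.074 × 3.30 = 6.8 points. If one patient per arm is lost (17 v 5): 2.086 × 7 × √(1/17 + 1/5) = 7.4 points.

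**5. Precision, adjusted for baseline.** Assume equal SDs at baseline and Day 43 and SD of change 7. The residual SD is 7 × √((1 + ρ)/2). Chance imbalance in a normally distributed baseline inflates the expected variance by 1 + 1/20. Half-width = t(21) × residual SD × 0.4714 × √1.05, with t(21) = 2.080.

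| ρ (assumed) | Residual SD | Half-width | Change from 6.84 |
|---|---|---|---|
| 0.5 | 6.06 | 6.1 | 11% narrower |
| 0.8 | 6.64 | 6.7 | about 2.5% narrower |
| 0.9 | 6.82 | 6.85 | none |

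Adjustment therefore buys little precision. Its use here is to correct for chance baseline imbalance, which can be large with 6 placebo patients.

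**The case against.** The strongest reply is that the plan is consistently descriptive and does what it says. The objective is safety, tolerability and pharmacokinetics. FEV1 in CF patients is exploratory and worded as change from baseline (Protocol 6.3); only the exacerbation rate is worded against placebo. Protocol 7.2 gives placebo the role of reducing bias in assessing safety and tolerability. Placebo is summarised beside active at each timepoint, so a reader could form the unadjusted difference from the planned n, means and SDs. By-subject listings would even let someone fit an adjusted one.

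Most of this stands, and it limits the point to an improvement. It rules out the inference that a promised comparison was dropped: none was promised. It does not remove the case for adding the estimate. A difference worked out afterwards by readers is not pre-specified, and nothing in the plan tells them how imprecise it is. Nor does a descriptive plan exclude intervals: SAP 9.7.4 already reports 90% confidence intervals for the dose-proportionality slope.

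A reader might also infer that the >80% is wrong, or that Cohort 6 fails a claim of power against placebo. The documents do not support this. The sentence takes baseline as its reference, names no comparator, and reproduces on the 18 active patients. Reading 7 as the SD of the change is also the natural choice. Cohort 6 admits ppFEV1 from 40 to 90%, and if values were spread evenly over that range the single-visit SD would be 50/√12, about 14.

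**Conclusion.** The point holds as an inexpensive improvement to an exploratory endpoint. Cohort 6 is randomised, blinded, sized on Day 43 ppFEV1 and intended to assess efficacy, yet its plan contains no randomised ppFEV1 estimate or interval at that visit. The stated power is sound as a within-group figure: 81.5%, assuming a two-sided one-sample t-test, 18 active patients and SD of change 7. Against placebo the same inputs give about 31%, with an unadjusted 95% half-width of about 6.8 points around a 5-point target.

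The unstated test, n, sidedness and SD definition are missing detail. On their own they would not amount to a flaw, and they do not show that the cohort is the wrong size. Primary and secondary endpoints, stopping rules and dose escalation are unaffected.

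**What to change.** 1. **SAP 9.6.1 and 4.1.** Add the Cohort 6 Day 43 difference in ppFEV1 change from baseline, active minus concurrent (Cohort 6) placebo, adjusted for baseline ppFEV1, with a 95% CI and no p-value, labelled exploratory. In SAP 4.1, list baseline ppFEV1 as the covariate for this one estimate, and give chance baseline imbalance as the reason. Do this before Cohort 6 is unblinded.
2. **SAP 3.2.** State that the >80% is a within-group figure for change from baseline, with the test, n, sidedness and SD definition the sponsor actually used, and that no test is planned. Add that the unadjusted 95% CI half-width for the 18 v 6 difference is about 6.8 points if the SD of change is 7 (adjusted: about 6.1 to 6.9). Protocol 12.1 can be aligned at the next amendment made for other reasons.

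The cost is a few sentences and one added model, with no new patients, visits or data. No resizing and no power figure against placebo are needed. The drawback is a wide interval with only 6 placebo patients, which adjustment will hardly narrow; stating that width in advance guards against over-reading it.
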